11.3.1 Handling of tissue at Cancer Institute of New Jersey Functional Genomics Facility

Clinical samples will be sent to:

[name] (or designate)
Manager
Functional Genomics Facility, Cancer Institute of New Jersey
[name], Robert Wood Johnson Medical School, [name]
[contact]

1. Extraction of total RNA

Total RNA from fresh frozen tissues will be extracted using RNeasy mini kit (QIAgen) according to the manufacturer's instructions. Total RNA from FFPE samples will be extracted using RNeasy FFPE kit (QIAgen). Concentration of RNA will be measured using Qubit 2.0 fluorometer (Invitrogen) and the quality will be examined with RNA 6000 Nano assay kit and Bioanalyzer 2100 (Agilent).

2. Extraction of Genomic DNA

Genomic DNA from fresh frozen samples will be extracted using DNeasy blood and Tissue kit (QIAGEN) according to the manufacturer's instructions. Genomic DNA from FFPE tissue samples will be extracted using QIAamp DNA FFPE Tissue Kit (QIAGEN). The concentration genomic DNA will be measured using Qubit 2.0 Fluorometer (Invitrogen) and the quality will be assessed with Agarose gel electrophoresis.

3. RNA Seq library preparation from Fresh frozen sample

RNA seq library will be constructed using Illumina TruSeq RNA sample preparation v2 protocol and the pooled libraries will be sequenced on the Illumina HiSeq 2000.

4. RNA Seq library preparation from FFPE sample

RNA seq library will be constructed using ScriptSeq complete gold kit (Epicentre) and the pooled libraries were sequenced on the Illumina HiSeq 2000.

5. Whole-exome sequencing

Whole-exome sequencing will be carried out using Illumina TruSeq Exome Enrichment protocol. Whole genome library will be constructed first using Illumina TruSeq™ DNA Sample Preparation v2 protocol. The fragmented DNA from each sample will be then enriched with TruSeq Exome enrichment protocol. Enriched fragments will be amplified using PCR. The bar coded libraries will be examined by Qubit for DNA amount and Agilent Bioanalyzer for DNA fragment size distribution, then diluted to appropriate molar concentration. Pooled libraries will be sequenced on the Illumina HiSeq 2000.

6. Cluster Amplification and Sequencing

Cluster amplification of denatured templates will be performed on cBot according to the manufacturer's protocol (Illumina) using HiSeq 2000 v2 cluster chemistry and flowcells. Flowcells will be sequenced on HiSeq 2000 using HiSeq 2000 v2 Sequencing-by-Synthesis Kits, then analyzed using RTA v1.10.15. or RTA v.1.12.4.2. Raw sequencing data will be processed into read sequences and base quality scores using the standard Illumina pipeline.

7. Validation Experiments

RNA seq data will be validated with QPCR. TaqMan probes and primers (ABI) for selected genes will be used for validation purposes.

DNA seq data will be validated with selected mutations using 1 to 20 ng genomic DNA. TaqMan SNP genotyping assay (ABI) will be used for the validation studies.

QPCR will be performed on the Stratagene Mx 3005P QPCR machine (Agilent) according to manufacturer's instructions.

11.3.2 Process at Cancer Institute of New Jersey Bioinformatics

DNA and/or RNA sequencing will be performed using established procedures at Cancer Institute of New Jersey, including standard protocols for DNA/RNA extraction, library preparation, and sequencing on Illumina HiSeq 2000 or similar technology.

Mutational status of each sample can be determined from both DNA and RNA sequencing, while gene expression may only be detected from RNA sequencing. We will aim for at least 50X coverage during DNA sequencing or at least 20 million reads during RNA sequencing. We have previously shown that latter is sufficient for unambiguous detection of HPV infection in known hosts, such as HeLa cell lines.

Genomic analysis will be performed using established pipelines at the Cancer Institute of New Jersey. Initial read alignment to the reference hg19 human genome will be done using BWA,

Bowtie2 and/or TopHat packages. Low quality reads will be filtered using standard Illumina protocol, allowing for minimum phred score of 25 per base. Genomic variants, including single nucleotide variants, and small insertions and deletions, will be called using GATK package following Broad Institute Best Practices Variant Detection protocol. Larger deletions and insertions, including exon and whole gene amplifications, will be analyzed based on changes in coverage using in-house pipelines. Changes in gene expression levels will be analyzed using Cufflinks, IPA, as well as in-house tools and pipelines that are part of local package iSeek. All detected variants and changes in gene expression will be compared with known databases, such as COSMIC, TCGA, IPA, and others.

12. Pharmaceutical Information

12.1 Investigational Agents

There are no investigational agents involved in this study.

12.2 Commercial Agents

Product description: Cetuximab is commercially available from Merck, IMCLONE. In this protocol cetuximab is not supplied, and is paid for by the patient or his insurance company.

Preparation: Erbitux® (cetuximab) is supplied at a concentration of 2 mg/mL as a 100 mg/50 mL, single-use vial or as a 200 mg/100 mL, single-use vial as a sterile, preservative-free, injectable liquid. It should be prepared as for standard preparation as per the package insert. Store vials under refrigeration at 2° C to 8° C (36° F to 46° F). **Do not freeze.** Increased particulate formation may occur at temperatures at or below 0° C. This product contains no preservatives. Preparations of Erbitux in infusion containers are chemically and physically stable for up to 12 hours at 2° C to 8° C (36° F to 46° F) and up to 8 hours at controlled room temperature (20° C to 25° C; 68° F to 77° F). Discard any remaining solution in the infusion container after 8 hours at controlled room temperature or after 12 hours at 2° C to 8° C. Discard any unused portion of the vial.

Route of administration:

- Premedicate with an H1 antagonist (eg, 50 mg of diphenhydramine) intravenously 30–60 minutes prior to the first dose; premedication should be administered for subsequent Erbitux doses based upon clinical judgment and presence/severity of prior infusion reactions.
- Administer 400 mg/m² initial dose as a 120-minute intravenous infusion followed by 250 mg/m² weekly infused over 60 minutes.
- Reduce the infusion rate by 50% for NCI CTCAE Grade 1 or 2 infusion reactions and non-serious NCI CTCAE Grades 3–4 infusion reactions.
- Permanently discontinue for serious infusion reactions. Withhold infusion for severe, persistent acneform rash. Reduce dose for recurrent, severe rash.

Expected toxicities: The most common adverse reactions (incidence $\geq 25\%$) are: cutaneous adverse reactions (including rash, pruritus, and nail changes), headache, diarrhea, and infection. Refer to the package insert for a complete list of toxicities.

Drug Interactions: No known drug interactions with cetuximab.

13. Data Collection and Records to be Kept

13.1 Case Report Forms

A subset of the NCI's CTMS case report forms, in electronic format (e-CRFs) will be utilized. Completion of the e-CRFs will be done in accordance with the instructions provided by Cancer Institute of New Jersey, the coordinating center in a study-specific data capture plan. Electronic CRFs will be submitted to the OHRS via Cancer Institute of New Jersey's On-line Clinical Oncology Research Environment (ONCORE). The e-CRFs are found in the study specific calendar that has been created in ONCORE. The system will prompt the user to the forms that are required based upon the patient's enrollment and treatment dates.

The Principal Investigator will be responsible for assuring that all the required data is entered onto the e-CRFs accurately and within 2 weeks of the date in which the previous cycle was completed.

Periodically, monitoring and/or auditing visits will be conducted by staff from the Coordinating Center. The Principal Investigator at each participating center will provide access to his/her original records to permit verification data entry.

Case report form completion instructions and training will be provided to each participating institution before study activation at the participating institution.

13.2 Research Charts

A research chart will be maintained for each patient enrolled. Copies of the most significant study source documents will be maintained in the research chart. Examples of source document copies that will be maintained in the research chart include: signed informed consent form, documents that verify eligibility, demographics, time to progression and survival. This information will be updated on a prospective basis and will be confidentially maintained at the OHRS.

14. Data and Safety Monitoring

Monitoring of this study will occur in accordance with the Cancer Institute of New Jersey's NCI approved Data and Safety Monitoring Plan (DSMP). An "initiation audit" will be conducted at Cancer Institute of New Jersey in accordance with the DSMP following

enrollment of the first two (2) or three (3) patients. Subsequent audits will occur on an annual basis prior to annual IRB continuing review, if the findings from the initiation audit were satisfactory. More frequent audits of patient data and study conduct will occur if necessary. All centers will be monitored at least quarterly and audited annually. Prior audit findings and/or situations that may arise during the course of the study will determine the need for more frequent auditing. All audit findings will be reported to Cancer Institute of New Jersey's Human Research Oversight Committee and the PI.

15. IRB Approvals

This protocol will enroll patients from Rutgers New Jersey Medical School and Rutgers Cancer Institute of New Jersey. Some molecular correlate studies will be performed at Rutgers Cancer Institute of New Jersey.

16. Statistical Considerations

16.1 Primary Hypothesis

The primary hypothesis is that patients who respond to neoadjuvant cetuximab and go on to receive concurrent cetuximab RT will have improved 2 yr locoregional control compared to unselected patients who receive cetuximab RT ie the cetuximab RT arm in the seminal Bonner randomized trial.

16.2 Sample Size Justification

The sample size justification is based on the primary hypothesis that patients who respond to neoadjuvant cetuximab will have at least a 25% greater two-year rate of locoregional control, compared to historical data- in the seminal Bonner randomized trial, patients treated with cetuximab and radiotherapy (but completely unselected) had a 50% locoregional control rate. We feel an improvement of 25% in LRC is very reasonable given the huge difference that rash made in the Bonner trial- of those patients receiving cetuximab RT, patients who developed a significant rash had OS of 68.8 months vs 25.6 months for those w no or minor rash; HR 0.49, 0.34–0.72; p=0.002.

We assume patients will be accrued uniformly over three years and then followed for an additional two years past the accrual period (after the last patient's accrual). Assuming no loss to follow-up and exponentially distributed event times, we used an exponential MLE one-sided test to detect an increase in locoregional control rate from 50% to 75% for sample size calculation. It would require 16 cetuximab responders to provide 80% power to detect at least an improvement of 2 yr LRC from 50% to 75% compared to historical controls, with the use of one-sided test at the 0.05 significance level. We assume 60% of accrued patients will respond to neoadjuvant cetuximab. Therefore, a total of 27 total patients are required. A one-sided log-rank test to compare 2 yr LRC of the current study with the historical control will be performed for the primary hypothesis.

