Is combining cisplatin, cetuximab RT (trimodality therapy) better than cisplatin RT? RTOG 0522 looked at this exact question in patients with stage III-IV carcinoma of the oropharynx, larynx, and hypopharynx received The experimental regimen (Arm A) consisted of

a loading dose and 6-7 weekly doses of cetuximab given in conjunction with the control arm (B) of 70-72 Gy (6 weeks) + 2 cycles of cisplatin (q3 weeks). At 2.4 years, there were no significant differences in progression-free survival (HR [A/B]: 1.05, 0.84-1.29; $P=0.66$; 2-Y rates: 63% vs. 64%), the primary endpoint, or in overall survival (HR: 0.87, 0.66-1.15; $P=0.17$; 2-Y rates: 83% vs. 80%). Though only out in abstract form, as HNSCC recurrences usually occur early, this is almost certainly going to be a negative trial. Therefore, there is no rationale at this point for attempting a protocol using trimodality therapy. Per personal communication with [name] (PI of RTOG 0522), he thinks that the reason that this was a negative trial was that both cisplatin and cetuximab have the same mechanism of action: disabling of DNA repair pathways after radiation.

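### The 80% power with 16 responders rests on a constant hazard out to year 5, and the log-rank test has no stated reference curve or data cut-off, so it may miss either its 5% level or its 80% power

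*Combined protocol and SAP*

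**What the plan says.** Section 16.2 gives the sizing model: "Assuming no loss to follow-up and exponentially distributed event times, we used an exponential MLE one-sided test". The rest of that sentence ties the model to sizing and sets the target as LRC of 75% against 50%. The follow-up assumption is "We assume patients will be accrued uniformly over three years and then followed for an additional two years past the accrual period", so individual follow-up runs from 2 to 5 years. The result is "It would require 16 cetuximab responders to provide 80% power". The test is one-sided at 0.05, and with 60% responders the total becomes 27 patients.

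The same section names a different procedure for the analysis: "A one-sided log-rank test to compare 2 yr LRC of the current study with the historical control will be performed for the primary hypothesis". For that control the plan gives one number, 50% LRC at 2 years in the cetuximab-radiotherapy arm of the cited randomized trial. Neither 16.2 nor 16.5 says what curve the log-rank test uses or when each patient's data stop.

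Three other places bear on this. Section 2.1, discussing another trial, reasons that "as HNSCC recurrences usually occur early, this is almost certainly going to be a negative trial". Section 4.1 sets a minimum of 2 years of follow-up. The evaluation table in Section 6 schedules three-monthly visits for 2 years after radiotherapy, with no later column except after failure.

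**The concern.** A one-sample log-rank test compares observed failures with the number a reference curve predicts over each patient's follow-up. The only curve shape in the plan is the exponential used for sizing. Through 50% at 2 years, it keeps predicting failures at the same rate to year 5. If failures in fact become rare after year 2, every controlled patient followed longer adds predicted failures that do not occur. The test then reads length of follow-up as benefit.

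At stake is the only powered comparison in the study, in 16 patients, which the protocol hopes will lead to a larger trial. Used past year 2, the exponential reference may not hold the 0.05 level. Stopping near year 2 protects the level, but the stated power no longer applies.

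**Working it through.** **Inputs.** From 16.2: one-sided 0.05; 80% power; LRC 50% against 75% at 2 years; uniform accrual over 3 years plus 2 years; no loss to follow-up; 16 responders; 60% response. Assumed here, because the documents give no figure: the failure hazard after year 2.

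**1. The plan's own figure.**
- Hazards: λ0 = ln 2 / 2 = 0.3466 and λ1 = −ln 0.75 / 2 = 0.1438 per year (ratio 0.415).
- Probability of an observed event: p = 1 − [exp(−2λ) − exp(−5λ)] / (3λ), giving p0 = 0.689 and p1 = 0.391.
- Cube-root-of-hazard scale: n = [(1.645·λ0^⅓/√p0 + 0.842·λ1^⅓/√p1) / (3(λ0^⅓ − λ1^⅓))]² = (2.097 / 0.535)² ≈ 15.3, rounded up to 16.
- The 2-year-survival scale gives 15.28, also 16. Power at 16 is 0.815 to 0.818, and 16/0.6 = 26.7, so 27 patients.

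The stated figures therefore reproduce with 2 to 5 years of follow-up at constant hazard. (Other scales give 15 to 19; the plan does not name its scale.)

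**2. What the exponential curve predicts later.** 0.5^(3.5/2) = 0.297 at 3.5 years and 0.5^(5/2) = 0.177 at 5 years.

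**3. Mechanism, in the extreme case of no failures after year 2.** By year 2, 16 × 0.5 = 8 failures are both observed and expected. The 8 controlled patients are then followed for 1.5 more years on average, adding 8 × 1.5 × 0.3466 = 4.2 expected failures and none observed. So O = 8 against E = 12.2, and (8 − 12.2)/√12.2 is about −1.2 on average, although 2-year LRC is exactly 50%.

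**4. Error rate, exponential reference, data used to year 5.** Simulation: 200,000 trials per row, n = 16, follow-up uniform on 2 to 5 years, true 2-year LRC 50%, rejection when (O − E)/√E < −1.645.

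| Hazard after year 2 (assumed) | Rejection rate |
|---|---|
| same as before year 2 (0.347/year) | 3.6% |
| 75% of it | 6.7% |
| 50% of it | 12% |
| 0.15/year | 14% |
| 0.10/year | 19% |
| 0.05/year | 25% |
| 0 | 33% |

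Other shapes with 50% at 2 years fall in the same band: Weibull with shape 0.8, 0.5 and 0.3 gives 6%, 11% and 14.5%; a cure plateau of 30%, 40% and 48% gives 11%, 17% and 23%. If the exponential MLE test were itself the analysis, no late failures would give up to about 39%.

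**5. A reference of the right shape.** If the log-rank reference follows the true curve, the error is 3.4% to 3.7%. Power is 79% at constant hazard and falls to about 63% with no late failures.

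**6. Data stopped at or near 24 months.**
- At 24 months: log-rank error 3.8% and power about 62%; exponential MLE error about 5% and power about 67% to 68%. About 22 responders would be needed for 80% on the MLE scales of step 1 (22.1 and 21.9).
- At 2.25 years (about 3 months of treatment plus the 2-year visit calendar): log-rank error about 4% to 6% across the late hazards in step 4; power 66% at constant hazard.
- Exact binomial, 16 responders: P(X ≥ 12 | 0.5) = 2517/65536 = 0.038, while 11 or more would give 0.105. Power P(X ≥ 12 | 0.75) = 0.63.
- Kaplan-Meier with complementary log-log limit, complete follow-up: 12/16 gives a one-sided 95% lower limit of 0.75^exp(1.645 × 0.502) = 0.519, and 11/16 gives 0.456. The decision rule is the same as the binomial.
- Exact binomial, 23 responders, 16 or more controlled: level 0.047, power 0.804. At 60% response, 23/0.6 = 38.3, so 39 patients.

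**The case against.** The strongest reply is that 16.2 ties the exponential model and the MLE test to the sample-size calculation only. The named primary test is a log-rank test, which needs no constant hazard, and its comparator is a published trial arm whose curve could serve as the reference. Step 5 shows no inflation in that case. The endpoint is 2-year LRC throughout, and the only scheduled visits end 2 years after radiotherapy, where the error is near nominal. The remark about early recurrence concerns another trial's result and gives no rate.

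Most of this stands. A reader might infer that the primary test itself assumes a constant hazard to year 5, and so carries a false-positive rate of 14% to 33%. The documents do not support that. They leave the reference curve and cut-off open, they schedule no visits past 2 years after radiotherapy, and milder late slowing gives 7% to 12%. The 33% end needs no late failures at all.

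The reply does not rescue the stated power. The 80% comes from constant-hazard follow-up averaging 3.5 years, and each route that protects the level when recurrences are early (a correctly shaped reference or a 24-month cut) leaves less than 80%.

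**Conclusion.** The concern holds conditionally, and the gap is more than missing detail. As written, 16.2 does not secure both a one-sided 0.05 level and 80% power for 2-year LRC if recurrences are early.

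- With the exponential reference and data past year 2, the error rises from about 4% to roughly 7% to 33%. This depends on a reference the plan does not state and on assumed late hazards.
- With data stopped at or near 24 months, the error is about 4% to 6%, and power with 16 responders is about 62% to 68%.

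This should be fixed, but it falls short of a mandatory change, because the size of the false-positive inflation rests on those two unstated inputs. The shortfall in power at 24 months does not: it follows from the plan's own figures.

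**What to change.** In 16.2 and 16.5, define the primary test at 24 months from a stated time origin. Censor every responder administratively at 24 months and compare LRC with 50% in one of two ways, chosen in advance:
- a Kaplan-Meier estimate with a complementary log-log one-sided 95% lower limit; or
- with complete follow-up, an exact binomial test (12 or more of 16 controlled; level 0.038, power 0.63).

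Report later failures descriptively, drop the constant-hazard extrapolation, and restate the power for 16 responders as about 63%.

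The change is to wording only and alters no visit or treatment. Its cost is the lower stated power. Restoring 80% with the exact test would take about 23 responders, or 39 patients at 60% response instead of 27; whether to do so is a separate decision for the sponsor.

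### Section 16.2 sizes on one test and analyses with another whose statistic and cut-off are not stated; with about 6 to 11 events, a 1.645 cut-off does not reliably give the stated 5%

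*Combined protocol and SAP*

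**What the plan says.** Section 16.2 gives the design test: "we used an exponential MLE one-sided test to detect an increase in locoregional control rate from 50% to 75% for sample size calculation". The level is set "with the use of one-sided test at the 0.05 significance level", and the result is stated as "It would require 16 cetuximab responders to provide 80% power". The accrual assumption is "We assume patients will be accrued uniformly over three years and then followed for an additional two years past the accrual period", with no loss to follow-up and exponential event times. A 60% responder share takes 16 responders to 27 patients.

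The same section then names a different test for the primary hypothesis: "A one-sided log-rank test to compare 2 yr LRC of the current study with the historical control will be performed for the primary hypothesis". It does not say whether the test is one-sample or two-sample, which variance is used, what the critical value is, or whether any small-sample method applies. Section 16.5 lists what will be reported and adds nothing on the test. Section 16.4 says the study is powered only for this outcome.

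**The concern.** The quoted 80% was worked out for one test, and another will decide the trial. Both would ordinarily be referred to a normal distribution, which is a rough guide with 6 to 11 events. At that size, the choice of variance alone moves the true significance level to either side of 5%.

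Two things are at stake in the only powered comparison. Power may be lost by running the test below its allotted level. And because the form is open, it could be settled after the data are seen, with a true level anywhere from about 3.6% to 7.8% under a nominal 0.05.

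**Working it through.** **Inputs (all from 16.2).** One-sided 0.05 (z = 1.645); power 80% (z = 0.842); n = 16; 2-year control 50% against 75%; accrual uniform over 3 years plus 2 years, so each patient is followed for 2 to 5 years; exponential times; no loss.

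**Hazards and events.**
- λ0 = −ln(0.50)/2 = 0.3466 per year; λ1 = −ln(0.75)/2 = 0.1438 per year.
- P(event) = 1 − (e^(−2λ) − e^(−5λ))/(3λ).
- Under 50%: 1 − (0.5000 − 0.1768)/1.0397 = 0.689, so 16 × 0.689 = 11.0 events.
- Under 75%: 1 − (0.7500 − 0.4871)/0.4315 = 0.391, so 16 × 0.391 = 6.3 events.

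**The plan's own figure.** Take the exponential MLE on the cube-root scale, with the variance under each hypothesis:
- λ0^(1/3) = 0.7024 and λ1^(1/3) = 0.5240; difference 0.1785.
- Per-patient SDs: 0.7024/(3√0.689) = 0.2821 and 0.5240/(3√0.391) = 0.2794.
- n = [(1.645 × 0.2821 + 0.842 × 0.2794)/0.1785]² = 15.3, so 16. Approximate power at 16 is 81.5%.
- 16/0.60 = 26.7, so 27.

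The stated 16 and 27 reproduce. The log-hazard scale gives 14.3 (15), and the usual one-sample log-rank formula gives 14.8 (15).

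**True size and power at 1.645.** These come from simulation with n = 16 and at least 1,000,000 trials per hypothesis. O is the observed number of events, and E is λ0 times total follow-up.

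| Statistic | Size | Power |
|---|---|---|
| (E−O)/√E | 3.6% | 78.7% |
| (E−O)/√((E+O)/2) | 5.5% | 84.1% |
| (E−O)/√O | 7.8% | 88.0% |
| Signed-root likelihood ratio | 4.9–5.0% | about 83% |
| Cube-root exponential MLE | 4.6–4.9% | 81.9–82.6% |

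The signed-root statistic is sign(E−O) × √(2[O ln(O/E) − (O−E)]), with the first term taken as 0 when O = 0.

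**Calibrated.** The cut-off that gives (E−O)/√E a true 5% is about 1.51, and power there is about 83%. That is about 4 points above 78.7%. Once calibrated to 5%, the (E−O) forms and the likelihood ratio all have about the same power, so their differences at 1.645 are differences in level.

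**Sensitivity to follow-up.** If times are cut at 2 years, (E−O)/√E has size 3.7% and power of about 62.6%, against about 67.7% when calibrated (cut-off about 1.48).

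**Sensitivity to the reference.** Assume the historical 50% has a sampling SD of 3.5 points (√(0.25/208) = 0.035; 208 is the number of cetuximab patients with rash information in the section 2.1 table). The size is then about 4.5% for (E−O)/√E at 1.645, and about 6% for either the calibrated version or the likelihood-ratio test. With an SD of 5 points the figures are about 5.4% and 7%.

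**The case against.** A reader might infer that the planned test runs at 3.6% instead of 5% and so throws away 4 to 5 points of power. The documents do not support that. The 3.6% belongs to (E−O)/√E at 1.645, and 16.2 commits to neither. Two other variance forms exceed 5%, and a cube-root exponential test, which reproduces the 16, comes close to 5% with power above 80%. So a conservative approximation is not a general property of this plan.

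The benchmark matters too. The plan promises 80%, and the standard form delivers 78.7%, a shortfall of 1.3 points. The 4-point loss is relative to a calibrated test that the plan never claimed to use. One more responder (17) would give about 81% at 1.645, and the responder count will vary by more than that around the assumed 60%. Sixteen is not shown to be wrong.

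Nor is recalibration free of cost. The documents give the historical control as a single value, without a curve or an interval, and 16.6 concedes that HPV comparability is hard to judge. If the 50% is uncertain, the conservative form's slack absorbs part of that error, and the calibrated test exceeds 5%.

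A two-sample comparison could also be meant. An illustrative run against 208 assumed exponential controls gives size 3.8% and power of about 76%, but the documents contain no control event times, so nothing should rest on it.

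These objections stand and limit the point. They leave untouched that the analysis test is under-specified and that, with so few events, its specification determines its level.

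**Conclusion.** The point holds in a modest form. Section 16.2 does not fix the statistic or cut-off for its primary test, and at 16 responders the normal cut-off gives a true size between about 3.6% and 7.8%, depending on a choice left open. Under the standard form the error is in the safe direction: a positive result remains valid, and power is about 1 point below the stated 80%. About 4 points are recoverable by running at a true 5%.

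These figures assume exponential times, the plan's accrual and full follow-up, no loss, exactly 16 responders, and a historical 50% treated as known. For a non-randomized pilot this is a refinement, but it concerns the only powered comparison and the remedy is cheap.

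**What to change.** In 16.2, name one statistic for both sizing and analysis, fixed before the data are seen. Either:

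- the one-sample signed-root likelihood-ratio test on observed versus expected events at 1.645 (size about 4.9–5.0%, power about 83%); or
- the one-sample log-rank (E−O)/√E, with its one-sided 5% cut-off simulated under the fixed reference curve, using the actual number of responders and their actual censoring (about 1.51 for 16 under the plan's assumptions).

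State the reference curve and the follow-up used, and restate the power for the chosen test. If (E−O)/√E at 1.645 is kept, state its size as about 3.6% and its power as about 79%.

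Add a sentence that the 5% is conditional on the historical 50%: with an assumed SD of 3.5 points, size would be about 6% for either recommended test and about 4.5% for the conservative one. The investigators can then choose between the power and the slack openly.

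The cost is a few sentences and a short simulation, with no added patients or data.
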